5. * Describe any potential for direct benefits to participants in this study:

Participants are unlikely to benefit from this study as it is intended for feasibility and acceptability assessment only. However, some participants may experience prevention or reduction in their delirium which would be beneficial to their overall health and potentially decrease some of their healthcare needs.

6. * Describe any potential for direct social impact in this study . For example, any engagement with specific communities to respond to community-identified needs, or ways the study will strengthen the well-being of the specific communities if applicable:

This study will engage participants from both the VCU Health downtown campus (medical respiratory ICU) and participants at VCU's Community Memorial Hospital (general ICU) in rural, South Hill, Virginia. Participants at CMH are being targeting for enrollment given the rural nature of the hospital's location and difficulty in enrolling rural patients into clinical research.

7. Upload a supporting citation list if applicable:

Study Population

1. * Provide the maximum number of individuals that

- 1. May participate in any study interaction or intervention (Including screening, consenting, and study activities) AND/OR**
- 2. You obtain any data/specimens about (regardless of identifiability)**

2. If this is a multi-Center Project, what is the maximum anticipated number of subjects across all sites?

not applicable

3. * Provide justification for the sample size by explaining how you arrived at the expected number of participants and why this number is adequate for answering the research questions:

Our goal is to generate descriptive data examining the feasibility and acceptability of weighted blankets and the use of technology to recruit and support clinical research in a rural patient population.

Sample size is based on the literature regarding targets for pilot studies examining feasibility and acceptability. Our sample will consist of the following:

50 adult medicine ICU patient participants: 25 at VCU Medical Center (VCUMC) and 25 at VCU's Community Memorial Hospital (CMH).

50 legally authorized representatives (upper limit; one for each patient participant)

100 Nurses (upper limit; two for each patient)

100 Medical Providers (upper limit; two for each patient)

Total Enrolled Participants = 300

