Approximate number of additional individuals expected with study interaction to account for screening failures and individuals who are approached but elect not to participate:

125 patient participants approach but are then Screening Failures

75 patient participants approached but who Failure to consent/enroll

Total additional individuals with study interaction: 200

Total number of individuals who may participate in any study interaction or screening: 500

Patient participants enrolled = 50

LARs maximum = 50

Nurse maximum = 100

Medical Provider maximum = 100

Screening failures = 125

Failure to enroll = 75

The estimate to account for screening failures and those who are approached, but elect not to participate based on the following data (and rounded up to capture the maximum number):

2019 average screen failure rate in global clinical trials was 36.3% - <https://blog.onestudyteam.com/3-ways-reduce-screen-failures-clinical-trials/#:~:text=As%20of%202019%2C%20the%20average,at%2036.3%25%20across%20therapeutic%20areas.>

2020 study showed 53% of those approached to participate in a clinical trial elect not to participate

<https://www.ncbi.nlm.nih.gov/pmc/articles/PMC8482053/#:~:text=Findings,of%20those%2C%2047%25%20participated>

4. * List the study inclusion criteria:

Patient Participant Inclusion:

18 years of age or older

Requiring ICU level of care

Have a primary medical diagnosis

Proficient in English language

LAR Inclusion:

18 year of age or older

LAR of patient enrolled in study

Proficient in English language

Healthcare Provider Inclusion:

18 year of age or older

Nurse, advanced practice provider, or physician of patient enrolled in study

Proficient in English language

5. * List the study exclusion criteria:

Patient Participant Exclusion:

-BMI less than 18.5

-Significant deficit in cognitive functioning that is not expected to improve due to an end-stage disease stage or permanent injury (e.g., end-stage encephalopathy, traumatic or anoxic brain injury, dementia)

-Known pregnancy

-Prisoner

-Presence of skin injury (e.g., surgical wound, pressure injury, moisture injury) in an anatomical location where additional weight/pressure of blanket could prevent healing and/or lead to an expansion of the injury. Patients with skin injuries to areas easily left uncovered by the blanket (e.g., hands, feet) can be enrolled with additional communication to clinical team to leave areas uncovered to prevent additional injury.

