Daily screening for inclusion/exclusion criteria will be conducted by the research team for patients admitted to VCUMC Medical Respiratory ICU (MRICU) and CMH ICU via EHR bedboards (via Epic) for both sites. For VCU Medical Center patients meeting inclusion criteria, a member of the study team will approach the patient at the bedside to review the informed consent form and answer any questions the patient may have before signing the consent. If the patient is not alert and oriented (as determined by the most recent physical assessment in the EHR and verified by the study team member bedside when engaging with the patient), the patient's LAR will be approached for consent, either in person in the intensive care unit (in the patient's room or in the dedicated family conference room to provide for privacy), or by phone (via number for LAR in EHR) if not available in person. The informed consent form will be reviewed with the LAR and questions answered by a member of the study team before signing. If the LAR does not answer when called, a message will be left via voicemail indicating that their family member may be eligible for participation in a clinical research study. They will be asked to call the study team member back at their convenience. If the LAR does not call back that day, a member of the study team will reach back out the next day. Failure to return a second message before the end of that day will indicate the desire to not have their family member participate and the LAR will not be contacted any further. The same procedures will occur for patients at CMH that meet study criteria. However, all in-person interactions planned for the VCU Medical Center site will be transferred to electronic means via Zoom. The designated study team member at CMH will bring the study dedicated iPad to the patient's bedside to engage with patients and/or their LAR. If the LAR desires, there will also be a dedicated private room at CMH where LARs can engage with the study team member reviewing the consent via Zoom. Although LAR consent will be required for enrollment of patients that are not alert and/or oriented, patient assent will be sought whenever possible.

5. * Does this study have a separate protocol document (i.e. a multisite or sponsor's protocol) that contains a detailed description of the study's methodology?

- Yes
 No

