6. * Since a separate protocol document is not uploaded, describe the proposed research using language understandable to those IRB committee members whose expertise is not scientific. The description must include:

1. A statement explaining the study design
2. A detailed description of all the procedures that will be followed to carry out the study, preferably in sequential order, and in sufficient detail that the study's methods could be replicated
3. The schedule and frequency of when and how procedures will be conducted (e.g. in person, online, phone, paper, etc.)
4. A description of all research measures/tests/interventions that will be used, including analyses/tests conducted on specimens/biological samples (if applicable)

See the help text for additional guidance

This is a descriptive feasibility and accessibility pilot study that will be conducted in a convenience sample of adult medicine ICU patients at VCU Health (VCUMC and CMH hospitals). Our sample will consist of 50 adult medicine ICU patients: 25 at VCUMC and 25 at CMH. Our goal is to generate descriptive data examining the feasibility and acceptability of weighted blankets and the use of technology to recruit and support clinical research in a rural patient population. Plans are for the results of this study to be used to support a larger, randomized clinical trial to be conducted in similar patient population (adult medicine ICU patients; rural and non-rural participants). Daily screening for inclusion/exclusion criteria will be conducted by the research team for patients admitted to VCUMC Medical Respiratory ICU (MRICU) and CMH ICU via EHR bedboards. Participants will be enrolled within 72 hours of ICU admission.

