8. * Select the processes for minimizing any potential perception of undue influence to participate, particularly when there is a pre-existing relationship between the participant and the researcher (e.g. treatment provider/patient; instructor/student; supervisor/employee, etc.):

- Having a 3rd person (family/friends, another study team member, etc.) present during the consent / assent discussion
- Having an independent advocate (e.g. advocate for decisionally impaired adults, wards) present during the consent / assent discussion
- Removing physical symbols of authority like white coats or police badges
- Sitting down beside the participant instead of standing over them
- If obtaining consent / assent in a clinical setting, letting patients sit instead of lie down (if they are able to)
- Moving to a more neutral location like a conference room
- Obtaining consent / assent after other services/interactions have been completed (e.g. after school or the clinic visit)
- Having a mandatory wait period for the participant to go home and think before they sign consent /assent
- Sharing the consent / assent discussion between two people (i.e. a clinician might be the best person to explain study procedures and risks, but then they could step out and let a research assistant finish the consent process)
- Other protection(s) not listed here describe below
- N/A: Requesting Waiver of Consent

9. * Describe the other ways the study team will minimize any potential perception of undue influence to participate:

The study team will emphasize that the trial is voluntary and standard of care will be performed with or without consenting.

10. * How much time will participants be given to make a decision:

The patient and/or their LAR will be given as much time as possible to make a decision, as long as it is within the indicated 72 hour time frame.

11. If applicable, describe the procedures for consenting children upon entering adulthood or participants who are no longer decisionally impaired:

Continual assent will be sought for any patient enrolled that is decisionally impaired. This will enable the team to ensure their assent if they become no longer decisionally impaired.

Consent Groups

1. * Enter a descriptive name for this consent / assent group:

Healthcare Provider

2. * Select all that apply to this consent / assent group:

Name

- Signed Consent by Participant

- Signed Parent/Guardian Permission or Legally Authorized Representative Consent

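### An unreturned second voicemail is read as unwillingness and no separate no-response category is described, so a refusal or consent rate could mix reachability with willingness

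*Combined protocol and SAP*

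**What the plan says.** Study Procedures, question 4, sets out the route for patients who are not alert and oriented. The LAR is approached in person, "or by phone (via number for LAR in EHR) if not available in person". If the call is not answered, a voicemail is left. "If the LAR does not call back that day, a member of the study team will reach back out the next day". Then: "Failure to return a second message before the end of that day will indicate the desire to not have their family member participate". Attempts to reach the LAR stop at that point. The same procedure applies at CMH, with in-person contact replaced by Zoom.

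Study Population, question 3, plans for 50 enrolled patients, 125 screening failures and "75 patient participants approached but who Failure to consent/enroll". That last group is a single category. The section supports its size with a cited figure for people who choose not to take part.

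Aim 2 concerns the feasibility and acceptability of remote technology for rural recruitment and participation. Study Procedures, question 6, plans descriptive statistics and a comparison of the two sites. No consent rate, refusal rate, denominator or success threshold is defined.

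**The concern.** The sentence does more than cap the number of calls. It says what silence means, and the meaning it assigns is a preference. Some of the people concerned may never have heard the message.

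In a feasibility study the distinction carries information. A refusal bears on acceptability; an unanswered message bears on the contact method. The two call for different changes in the larger randomized trial that this pilot is meant to support. The rule applies only to patients who need an LAR, and the section on decisionally impaired adults treats the patients most at risk of delirium as crucial to the aims. If LARs are harder to reach at one site than at the other, the site comparison would show a difference in apparent willingness that is really a difference in reachability.

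The distinction may also be impossible to recover later. Partial Waiver of Authorization, question 2, says that nothing about a person who chooses not to enroll is kept once accrual objectives are met.

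**Working it through.** **1. The plan's own counts.** Study Population, question 3, gives 50 patients, 50 LARs, 100 nurses and 100 medical providers: 50 + 50 + 100 + 100 = 300. Adding 125 screening failures and 75 not enrolled gives 300 + 125 + 75 = 500. Both totals reproduce.

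The 75 does not follow directly from the cited 53% who decline. With 50 enrolled, the number approached would be 50/(1 − 0.53) = 106.4, leaving 56.4, or 57 rounded up. The section says its allowances were rounded up to capture a maximum, so this is not an error. It does mean that the 75 is a headcount ceiling and not a forecast of refusals.

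**2. Direction of the effect.** Let E be the number who consent, R the number who are reached and decline, and N the number with no response after the second message. For simplicity, assume that everyone reached either consents or declines.

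| Quantity | No response kept separate | No response coded as refusal |
|---|---|---|
| Consent among those reached | E/(E + R) | E/(E + R + N) |
| Refusal share | R/(E + R) | (R + N)/(E + R + N) |

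Whenever E and N are both above zero, the coded consent rate is lower and the coded refusal share is higher. The size depends on N, for which the documents give no figure.

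**3. Overall yield.** Enrolled over approached is E/(E + R + N), whichever label N carries. On the planning counts it is 50/(50 + 75) = 50/125 = 40% in both cases, provided the same people count as approached under either label. Relabelling changes neither numerator nor denominator. What coding N as refusal does is make the consent rate equal to the yield, so that two different quantities become one.

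**4. Site comparison.** At each site the coded rate factors as

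E/(E + R + N) = [E/(E + R)] × [(E + R)/(E + R + N)]

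That is willingness among those reached, multiplied by the fraction reached. Two sites with equal willingness would still differ on the coded rate if their fractions reached differ. Without a count of N at each site, the factors cannot be separated.

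**The case against.** The best reply is that this is a rule for stopping contact. It answers a form question about the timing and frequency of recruitment attempts, and nothing in the text says how a non-responding LAR will be coded or analysed. No recruitment estimator exists to be biased. The Data Collection Spreadsheet and the REDCap fields may hold a suitable code. Some LARs will have heard the voicemail and chosen not to call, so refusal is sometimes the right reading, and calling them all unreachable would err the other way.

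Most of this stands. It makes the effect conditional and its size unknown, and it means that the replacement label must be neutral. It does not remove the sentence, which states that silence shows unwillingness, or supply the missing category.

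A reader might go further in three ways that the documents do not support.

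- **A numerical effect.** Treating some of the 75 as unreached gives, for example, 50/(125 − 15) = 45.5% or 50/(125 − 40) = 58.8% consent among those reached. But the 75 is a rounded-up ceiling for people approached, and the text does not say whether an LAR who was never reached falls within it. These figures are not projections.
- **A benchmark of 47%.** This is only the complement of the cited 53%, which was used to size the allowance. It is not a success criterion, so nothing turns on crossing it.
- **A contradiction over timing.** The consent section for patient participants (question 10) says "The patient and/or their LAR will be given as much time as possible to make a decision", but limits this to the 72-hour frame, in line with "Participants will be enrolled within 72 hours of ICU admission". That concerns time to decide; the voicemail rule concerns attempts to make contact. Two days of attempts can fit within 72 hours, and extending them would be a preference.

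**Conclusion.** The concern holds in a limited form. The plan equates an unreturned second message with a wish not to participate, and the available text gives no category that would keep the two apart. If dispositions are recorded on that basis, a refusal rate would be overstated, a consent rate among those reached understated, and the VCUMC versus CMH comparison could confuse reachability with willingness.

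The amount is unknown. The rule touches only patients who need an LAR, where that LAR is absent and returns neither message, and this number could be near zero. A difference between sites in reaching LARs is plausible but not quantified. Overall yield is unaffected.

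A reader might infer that the recruitment-feasibility estimate is biased downward. The documents do not support this: they define no such estimate, and failure to make contact is a genuine feasibility loss that belongs in the yield. The conclusion rests on dispositions following the stated rule and on the unavailable spreadsheet holding no separate code.

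**What to change.** Keep the two-message limit. Replace the sentence in Study Procedures, question 4, with: *No response by the end of that day will be recorded as no response, separately from declined, and the LAR will not be contacted further.*

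Keep an anonymised count of dispositions, tallied when each occurs. A count without identifiers fits the anonymisation option in Data Retention, question 1 (written for people who do not qualify), and the undertaking in Partial Waiver of Authorization, question 2, to keep nothing about individuals who choose not to enroll.

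Report, by site and by route (patient or LAR), the numbers eligible, reached, consented, declined and without response. Give two rates: enrolment among all eligible, and consent among those reached.

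The cost is one extra code in the screening record and a little more tabulation. The Review Setup page lists a continuing-review category limited to data analysis. If accrual has ended, the wording change comes too late; the report should then separate the groups where records allow, and otherwise state that it cannot.

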Once informed consent is obtained, medical-grade weighted blankets (equal to approximately 10% of the participants body weight up to 20lbs maximum) will be applied to participants by the bedside nurse for a minimum of 6 continuous hours nightly between 7pm-7am and additional hours as desired by the patient, their LAR, or the patient's clinical care team. Weighted blankets of various weights will be readily available on the nursing unit; the study team will communicate with the bedside nurse regarding what weight blanket will be used for each patient enrolled. Hourly rounding by a study champion will be utilized to document blanket use between the hours of 7pm-7am. Participants will remain enrolled in the study until they are withdrawn (either at participant request, administrative due to an adverse event, or at the request of the clinical team), or they are transferred from an ICU level of care. Data will be collected on: (1) feasibility and acceptability of weighted blankets; (2) feasibility and acceptability of technology to promote rural participation; (3) preliminary descriptive data and trends related to delirium, agitation, ventilator days, length of stay; and (4) participant demographics (see Data Collection Spreadsheet supporting document attached). A REDCap database the incorporates all data points needed to answer study aims will be developed with the assistance from the Wright Center Biostatistical Consulting Laboratory. Data analysis will include descriptive statistics and comparison statistics between VCUMC and CMH. Once the patient's participation ends (withdrawn or transferred from an ICU level of care), the patient (if alert and oriented), the patient's LAR, the patient's nurse, and the patient's physicians and/or advanced practice providers (APPs) will be asked to complete an electronic survey based on their experience with the weighted blanket use. Surveys will only be administered if a patient uses the blanket for at least one night. The survey will be in REDCap; no participant identifiers will be used. The survey will be opened by a member of the study team and brought to the participant on a study dedicated iPad. The study team member will remain in close proximity until the participant indicates they are done. At the time, the study team member will collect the iPad and ensure the survey has been closed. Who the patient's nurse and physicians/APPs are for the day will be determined by the ICU's electronic assignment board and/or care team noted in the EHR via the storyboard.

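### Staff survey respondents are chosen by assignment once participation ends, with no condition that they applied or observed the blanket, so the applying nurse can be missed and unexposed staff included

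*Combined protocol and SAP*

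**What the plan says.** Everything here is in the Combined protocol and SAP.

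- **Design.** Study Procedures, item 6: "This is a descriptive feasibility and accessibility pilot study", in a convenience sample of 25 patients at each of two hospitals.
- **Use.** The blanket "will be applied to participants by the bedside nurse for a minimum of 6 continuous hours nightly between 7pm-7am", with "additional hours as desired by the patient, their LAR" or the clinical team. Use is logged as follows: "Hourly rounding by a study champion will be utilized to document blanket use between the hours of 7pm-7am".
- **Survey timing and respondents.** Staff are surveyed when the patient is withdrawn or leaves ICU care. Item 6 fixes the respondents by assignment ("nurse and physicians/APPs are for the day will be determined by the"). The sources it names are the unit's staffing board and the care team listed for the patient in the health record.
- **Exposure condition.** "Surveys will only be administered if a patient uses the blanket for at least one night". This is a condition on the patient.
- **Staff eligibility.** Study Population, item 4, requires adult age, English proficiency and a role: "Nurse, advanced practice provider, or physician of patient enrolled in study". Item 5 excludes only those who are not active providers of the patient.
- **Numbers.** Study Population, item 3, allows up to two nurses and two medical providers per patient.
- **Linkage.** Active Internet Data Collection, item 2, keeps survey data apart from identifiers and participant numbers. Waiver of Some or All Elements of Consent, items 4 and 6, keeps only a count of completed surveys.
- **Analysis.** Study Procedures, item 6, plans descriptive statistics and comparisons between the two hospitals, without naming the variables.

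**The concern.** The staff survey is meant to show whether the blanket is acceptable to the people who have to use it. The selection rule points to whoever holds the assignment when participation ends, while the required work is done at night by the bedside nurse. A day nurse first assigned on the transfer day is eligible, as is a physician who never saw the blanket in place. The nurse who lifted and placed it every night need not be asked.

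Staff acceptability is part of Aim 1, and the results are intended to support a larger randomized trial. In justifying the consent waiver (Waiver of Some or All Elements of Consent, item 5), the protocol treats representative and provider feedback as essential to its aims. If unexposed staff answer, the staff result becomes a mixture of opinion from use and opinion at a distance, and a reader could not tell the proportions.

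**Working it through.** **1. Reproduce the stated counts.** Study Population, item 3: 50 patients x 2 nurses = 100; 50 x 2 medical providers = 100. With 50 patients and 50 representatives, 50 + 50 + 100 + 100 = 300, which agrees with the stated total. Per site, 25 x 2 = 50 nurses and 25 x 2 = 50 medical providers at most. These are ceilings.

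**2. Look for a staff-level exposure condition.**

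| Place | Condition on the staff member |
|---|---|
| Study Population, items 4 and 5 | Role, age, English, active provider of the patient |
| Study Population, item 3 | Up to two nurses and two medical providers per patient; shift not specified |
| Study Procedures, item 6 | Assigned on the day; use condition is on the patient |
| Consent Groups, Healthcare Provider, items 7 and 10 | In person, on the study iPad, completed or returned at once |

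None requires having applied or observed the blanket. Immediate in-person completion favours whoever is on shift when the team arrives.

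**3. Can exposure be recovered afterwards?** The hourly log and the assignment board together show who was assigned on nights of use. The survey responses carry no participant number, so they cannot be matched to either. Exposure can be recovered only if the form itself asks.

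**4. Size, as an illustration only.** The documents give neither the unexposed share nor the difference in acceptability between exposed and unexposed staff. Assume both, and take one response from each of 50 nurses at a site. The shift in the pooled percentage is the unexposed share x the difference.

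| Assumed unexposed share | Shift if the difference is 10 points | Shift if it is 20 points | Exposed responses of 50 |
|---|---|---|---|
| 0% | 0 | 0 | 50 |
| 10% | 1.0 | 2.0 | 45 |
| 25% | 2.5 | 5.0 | 37.5 |
| 50% | 5.0 | 10.0 | 25 |

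The direction is not known either.

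**5. Are respondents distinct persons?** Active Internet Data Collection, item 2, says the team will know whether each intended respondent completed the survey. Waiver of Some or All Elements of Consent, item 6, keeps only a count, and Populations with Special Considerations, item 2, says no record will show which providers took part. These statements need reconciling before staff results can be described as numbers of people.

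**The case against.** - **The forms are unseen.** The Documents section lists two staff forms, one on the provider's own experience and one on the provider's view of the patient's experience. They may already ask about exposure or offer a way to say the blanket was not observed. This stands, and it makes the second part of the fix conditional. It does not change whom the selection rule reaches.
- **The day is not defined.** Reading it as the exit day is an inference from the timing of an in-person survey. It is the natural reading, but the protocol does not say so.
- **Some exposure is likely.** Two nurses may answer for each patient, daytime use is allowed, an assigned blanket stays in the patient's room (Bio-Medical Device Details, item 3), and staff may decline or skip questions. These facts lower the risk without ensuring exposure. Framing the survey around the respondent's experience describes its content and does not select who is asked.
- **Staff who did not handle the blanket can hold useful views.** The clinical team can ask for extra hours or for withdrawal. This is fair, and such views should be kept and shown separately.
- **The question may be closed.** Review Setup, item 7, records a continuing-review category in which only data analysis remains. If that describes the study's status, only the reporting can change.

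A reader might also infer that repeat respondents make the site comparison of staff surveys anti-conservative. The documents do not support a figure for this: the comparison names no variables or test, and neither the number of responses per person nor their correlation is given.

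**Conclusion.** The point holds as a gap in the selection rule. Followed as written, the plan can leave out the nurse who applied the blanket and can include staff with no contact with it. Unless the forms ask, the two cannot be told apart afterwards. This rests on reading the day as the exit day and on the reviewed text, which does not include the staff forms or the Data Collection Spreadsheet.

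The size is unknown. If every respondent was exposed there is no distortion; the shifts of up to 10 points shown above come wholly from assumed inputs. A reader might go further and conclude that the staff acceptability data are invalid, or that most respondents will be unexposed. The documents support neither, and patient surveys, representative surveys and the hourly use log also inform Aim 1. The change is worth making because it is cheap and the measure matters to the next trial. Confidence is medium.

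**What to change.** **If surveys are still being collected**

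1. Within the cap of two nurses per patient, invite at least one nurse who was assigned on a night with logged blanket use, for example the most recent such night. The hourly log and the assignment board identify that nurse.
2. Unless the forms already have it, add one anonymous item asking whether the respondent applied or observed the blanket for this patient. It also covers physicians, advanced practice providers and daytime use, which the 7pm to 7am log does not record. Report staff acceptability among exposed respondents, and count and show the unexposed separately.

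**If collection is complete**

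3. State as a limitation that staff were sampled by assignment without confirmed exposure. Keep any comparison of staff responses between the two hospitals descriptive.

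**In either case**, reconcile the statements on tracking survey completion, and report results as forms unless distinct respondents can be counted.

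**Cost.** During collection: one survey item with IRB review of the edit, some approaches to night staff, who may have to be found after the patient has left, and fewer forms in the exposed summary. After collection: wording only. Anonymity is preserved throughout.
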